Risk Communication: Risk communication, in the form of comic books with accompanying read-along videos for the children (n=3) and videos for the parents (n=2) will be distributed in English and Spanish to all enrolled students within two weeks of completion of the ROSSEY RCT final assessment (December 2023). Three comic books will be distributed by mail and parents will be sent a password-protected link with the mailed comic to access the parent videos and comic book read-along videos. All intervention materials (i.e., children's comic books and parent videos) will be distributed after the final assessment of the larger ROSSEY RCT study is complete. The delay is to eliminate possible contamination of the RCT by siblings of comparison students who will receive the comic books as part of this ancillary study.

Outline of Early Learning Study Procedures

Follow-up Survey: We will contact parents 6 weeks after the risk communication intervention distribution. Parents will be asked to complete the follow-up survey either online or by phone. The surveys will ask for updates to their contact and demographic information, child's COVID-19 vaccination status, and child's SARS-CoV-2 mitigation behaviors and the secondary outcome measures.

Following the protocol from the ROSSEY RCT, the post assessment will take place over 6 weeks, allowing two weeks for final contact prior to closure. For EL participants with missing or phone numbers no longer in service, ROSSEY staff will contact the YSD to 1) determine if the student is still attending YSD, 2) find out school and teachers name to send a notice through the school to the parent letting them know we are trying to reach them. Students determined to still be enrolled at YSD, and are non-responders to the follow up survey, will receive an at home visit by ROSSEY staff as a final attempt to reach student and parent to complete survey. Follow-up assessment closure will take place one week after completion of home visits.

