ReOpening Schools Safely and Educating Youth (ROSSEY Study) – Early Learning Ancillary Study

Clinical Trials.gov : NCT05965323

June 30, 2022

STATISTICAL ANALYSIS PLAN

1. Introduction to the SAP

This statistical analysis plan (SAP) describes the plans for statistical analyses that will address the study's protocol objectives.

2. Study Schema and objectives

Purpose:	Evaluate if risk communication health education can increase uptake of COVID-19 mitigation measures, improve children's school attendance, and increase families' physical and mental well-being using a single-arm pre/post study.
Design:	A single-arm pre/post-study
Central Hypotheses:	Our central hypotheses are that students and parents who view the risk communications will be more likely to have increased COVID-19 testing and vaccine uptake.
Primary Objectives:	
• To determine if implementing three COVID-19 education comic books for children and two COVID-19 education videos for parents will increase COVID-19 testing and vaccine uptake in children.
Secondary Objectives:	
• To determine if implementing three COVID-19 education comics books for children and two COVID-19 education videos for parents will increase physical activity, improve sleep, increase emotional regulation in children.• To determine if implementing three COVID-19 education comics books for children and two COVID-19 education videos for parents will increase physical activity, improve sleep, decrease depression and anxiety in parents
Population:	Children ages 3-5 enrolled in the Early Learning program in Yakima School District
Study Size:	Early Learning is an ancillary study with no defined sample size. We will enroll and recruit participants for a total of eight weeks
Primary Outcome Measurements:	
A. COVID-19 testing data available through self-reported surveyB. COVID-19 vaccine data available through self-reported survey
Study Duration:	11 months – September 2022- August 2023

3. Study Design

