The ancillary study runs parallel with the larger ROSSEY RCT. Recruitment, enrollment, and baseline assessment are expected to last two months (September-November 2022). Enrolled participants will not receive the comic book and parent video series until after completion of the ROSSEY RCT Post 1 follow-up Survey to not bias the data of older siblings participating in the ROSSEY RCT. A follow-up assessment for Early Learning participants is anticipated to take place 10 months after the launch of recruitment (July-August 2023)

4. Sample size and power

Early Learning is an ancillary study of 50 participants. We will enroll and recruit participants for a total of eight weeks.

Enrollment Criteria

Parent/Guardian eligibility criteria for participation in the study include:

- Must have a child attending the Early Learning Program in the Yakima School District
- Must be able to provide informed consent and legal guardian assent either virtually, on the telephone, or in-person.
- Must have a permanent mailing address available for study staff to mail necessary materials OR a working email address.

5. Population and Data Source

Participants enrolled in the ROSSEY Study: 50 children and parents from the Yakima School District. Any participants subsequently found to be ineligible will be removed. The data sources for the primary analyses are COVID testing results received from the school administration and the survey data as entered in REDCap. The COVID vaccination status data is obtained through the parent and child surveys, completed in REDCap.

6. Presentation of analyses

For each of the continuous outcomes (including the primary outcome), the mean and standard deviation will be presented pre/post intervention and p value. For binary outcomes, the percentage and frequency of children in the outcome category of interest (e.g., percentage vaccinated) will be presented pre/post and p value.

7. Outcome Definitions

a. Primary Outcomes

The two co-primary outcomes of the trial are COVID-19 testing and COVID-19 vaccine uptake. COVID-19 data are captured through school testing and self-reported survey, and COVID-19 vaccine uptake data are captured through self-reported survey. All children and parent data will be included in the intention-to-treat analysis.

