COVID-19 testing: Health reports from the school are provided for the 2022-2023 school year that list positive covid test results of study participants with the date of testing and the school of attendance. Positive test results for COVID will be a binary, yes/no variable.

COVID-19 vaccine uptake: Parents are asked at enrollment to report their vaccination status and their child's vaccination status. At post survey, the parent is asked to report if they or their child have received any COVID-19 vaccine or booster since enrollment. Vaccination status will be a binary, yes/no variable.

b. Secondary Outcomes

Secondary outcomes for the trial include the following outcomes from the PROMIS – Pediatric and Parent Proxy Instruments. The PROMIS instruments used are Children's physical activity (PA), sleep, stress, depression, and anxiety. Parents' PA, sleep, stress, depression and anxiety. The final score is represented by the T-score, a standardized score with a mean of 50 and a standard deviation (SD) of 10.

The outcome measures will be collected at pre-and post-assessment.

8. Primary exposure definition

Receiving the educational materials: three comic books and two graphic motion videos.

9. Interim analysis plan

For this study, there was no interim analysis.

10. Multiple testing

We will adjust for multiple testing by controlling FDR.

11. Missing Data

We will inspect missing data mechanisms and the amount of missing data. We will conduct an additional sensitivity analysis with multiple imputations using multivariate imputation with chained equations (MICE) approach. We will report the amount of missing data and apply appropriate methods to account for the missing data.

12. Planned Statistical Analyses

a. Baseline Demographics

The baseline characteristics of enrolled participants will be summarized in a table.

b. Efficacy Analyses Overview

Pre/post-survey outcome analyses will be conducted after all participants have been contacted and the survey is closed with missing responses marked as loss to follow-up.

- 1) **Descriptive Analyses:** Positive COVID test results will be summarized by counts. Vaccine status and COVID testing results will be presented as counts and percentages. Continuous variables will be summarized by mean, standard deviation (SD), and median (IQR). Secondary outcomes will be compared using Chi-squared tests.

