- 2) **Primary Objectives:** The primary analysis of vaccine uptake and COVID testing will be conducted using a chi-squared test using $\alpha = 0.05$ and report pre/post changes over time.
- 3) **Secondary outcomes:** The secondary outcomes for the trial include measures from the PROMIS – Pediatric and Parent Proxy Instruments. The PROMIS instruments used are children's PA, sleep, stress, depression, and anxiety and parents' PA, sleep, stress, depression, and anxiety.

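### Two incompatible schedules are given, and under either one the vaccine outcome, counted from enrollment, mostly covers time before families receive the materials

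*Protocol*

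**What the plan says.** **Schedule in Protocol VI (Study Procedures).** Under Risk Communication, the materials are "distributed in English and Spanish to all enrolled students within two weeks of completion of the ROSSEY RCT final assessment (December 2023". Under Follow-up Survey: "We will contact parents 6 weeks after the risk communication intervention distribution". The post assessment runs for six weeks. Non-responders still enrolled in the district then receive a home visit, and follow-up closes one week after the visits end.

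**Schedule in Protocol I and SAP 2–3.** Enrollment and baseline run from September to November 2022. Distribution waits for the RCT's Post 1 survey, which is given no date and is a different milestone from the final assessment named in Protocol VI. Follow-up is anticipated for July–August 2023, and SAP 2 ends the study in August 2023.

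**Outcomes in the SAP.**
- Vaccine uptake (7a): "At post survey, the parent is asked to report if they or their child have received any COVID-19 vaccine or booster since enrollment". The variable is yes/no, and the SAP specifies no dose date.
- Testing: SAP 2 lists "COVID-19 testing data available through self-reported" survey, and SAP 7a says "COVID-19 data are captured through school testing and self-reported survey". The only source that 7a goes on to describe is the school: "Health reports from the school are provided for the 2022-2023 school year that list positive covid test results of study participants".
- PROMIS scores (7b): "The outcome measures will be collected at pre-and post-assessment".
- Analysis (12b): a chi-squared test for the two co-primary outcomes, which will "report pre/post changes over time".

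**The concern.** A single-arm pre/post study has no concurrent control. What links a change to the materials is mainly that the change comes after them, so the outcome window has to start at distribution or be split there. The SAP's vaccine window starts at enrollment, and distribution was deliberately delayed by many months. Applied as written, the rule counts a dose given in the months before the mailing as uptake following the comics and videos. The school reports have a related problem, because they are fixed to a school year that may end before anyone is exposed. Since the documents give two schedules, a reader also cannot tell how long the exposed period was. Both co-primary outcomes are affected.

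**Working it through.** **Inputs.** Enrollment September–November 2022 (Protocol I), taken as 1 September to 30 November 2022. Distribution within two weeks of a December 2023 assessment (Protocol VI), taken as 1 December 2023 to 14 January 2024 (31 December + 14 days). First contact at 42 days; surveys completed 42–84 days after distribution (six weeks plus the six-week window). The exact first and last days are assumptions; the months are the documents'.

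**The plan's own figure.** September 2022 + 10 months = July 2023, so the July–August 2023 follow-up date agrees with its stated interval. The conflict lies with Protocol VI.

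**Do the schedules fit together?** Under Protocol VI the survey opens between 1 December 2023 + 42 days = 12 January 2024 and 14 January 2024 + 42 days = 25 February 2024. That is 134 to 178 days after 31 August 2023, the SAP's study end. They do not fit.

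**Vaccine window, December 2023 schedule.** Pre-exposure share = (days from enrollment to distribution) / (days from enrollment to survey).
- Days before exposure: 30 November 2022 to 1 December 2023 = 366; 1 September 2022 to 14 January 2024 = 500.
- Lowest share: 366 / (366 + 84) = 366/450 = 81%.
- Highest share: 500 / (500 + 42) = 500/542 = 92%.
- Home visits are planned but their length is not given. Assuming three more weeks, the lowest share is 366 / (366 + 105) = 78%; assuming four, 366 / (366 + 112) = 77%.

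**Vaccine window, July–August 2023 schedule.** The Post 1 date is not stated, but Protocol VI's six-week lag allows back-calculation: 1 July − 42 days = 20 May 2023, and 31 August − 42 days = 20 July 2023.
- Lowest share: 30 November 2022 to 20 May 2023 = 171 days; 171 / (171 + 84) = 67%.
- Highest share: 1 September 2022 to 20 July 2023 = 322 days; 322 / (322 + 42) = 88%.
- This range leaves out home visits. If surveys after a 20 May distribution ran to 31 August (103 days), the lowest share would be 171 / (171 + 103) = 62%.

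**School reports.** Even if the 2022–2023 school year is stretched to 31 August 2023, it ends 92 days before 1 December 2023, so it holds no post-exposure days on the December 2023 schedule. On the July–August schedule, with an assumed school-year end of 30 June, it holds at most 41 days (from 20 May).

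**PROMIS, December 2023 schedule.** Baseline to survey is 366 + 42 = 408 to 500 + 84 = 584 days. The part after exposure is 42/542 = 8% to 84/450 = 19%.

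**The case against.** A reader who joins Protocol VI's mailing date to Protocol I's follow-up date might infer that the outcome was to be measured before the exposure. The documents do not support that. Each schedule taken alone puts follow-up after distribution. The July–August date is described as anticipated, and the SAP is dated June 2022, so it may simply be an old forecast. The date conflict is therefore a documentation error, although the protocol updated 1/03/24 still carries it. The vaccine window is a problem under either schedule.

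Three further limits stand.
- The questionnaire is not in the documents. One might infer that dose dates were not collected, but all that can be said is that the SAP specifies none.
- One might infer that testing has no post-exposure source. It has one: SAP 2 and 7a name self-report, and the Protocol VI follow-up survey covers mitigation behaviors, among which Protocol III counts testing. What is missing is the item and its recall window.
- The delay is deliberate and justified, because it protects the RCT from contamination through siblings. The long PROMIS interval follows from it and needs only a reporting caveat.

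The remedy also has limits. With about 50 families and 42–84 days there will be few post-exposure events. Vaccination status can only rise between distribution and follow-up, and windows before and after the mailing remain open to calendar trends. These points limit what the study can show. They do not justify counting pre-exposure doses as a response to the materials.

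**Conclusion.** The point holds and should be fixed before the results are interpreted. The two schedules, and the two RCT milestones that trigger distribution, cannot both be right. Under either, the vaccine outcome as defined mostly covers time before exposure: about 77–92% of calendar days on the December 2023 schedule (81–92% without home visits), and about 67–88% on the July–August 2023 schedule with the six-week lag. These ranges rest on the assumed calendar limits shown and, for the 77%, on an assumed four weeks of home visits.

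It is tempting to read these percentages as the proportion of doses that would be wrongly credited. The documents give no dose timing, so that proportion is unknown.

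For testing, the claim that the 2022–2023 school reports contain no post-exposure time is specific to the December 2023 distribution. On that schedule the survey is the only possible post measure, and the SAP has not defined it.

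**What to change.** 1. State one dated schedule and one RCT milestone (Post 1 or final assessment) in Protocol I, Protocol VI and SAP 2–3, and correct the study duration.
2. In SAP 7a, define vaccine uptake relative to the logged distribution date. Use dose dates to compare status at distribution with status at follow-up or, better, new doses in equal-length windows before and after distribution, which also shows the background rate.
3. If dose dates are not available, report uptake since enrollment as descriptive and do not attribute it to the materials.
4. Label the 2022–2023 school reports as pre-exposure and descriptive. Take post-distribution testing from a defined survey item whose recall starts at distribution. Later school reports that list only positives would not measure testing uptake.
5. Note in the report that PROMIS change spans the pre-exposure gap.

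**Cost.** Wording changes, the distribution date in the analysis file, and small changes to two survey items. If 1/03/24 means 3 January 2024, the survey opened 9 to 53 days later (12 January to 25 February) and the items could still be changed. If it means 1 March 2024, the survey was already open and step 3 may be all that can be done for vaccination. The price is few countable events, and parents having to recall or look up dose dates over 408–584 days (about 13–19 months) on the December 2023 schedule.

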ReOpening Schools Safely and Educating Youth (ROSSEY Study) – Early Learning Ancillary Study

Clinical Trials.gov : NCT05965323

June 30, 2022

STATISTICAL ANALYSIS PLAN

1. Introduction to the SAP

This statistical analysis plan (SAP) describes the plans for statistical analyses that will address the study's protocol objectives.

2. Study Schema and objectives

Purpose:	Evaluate if risk communication health education can increase uptake of COVID-19 mitigation measures, improve children's school attendance, and increase families' physical and mental well-being using a single-arm pre/post study.
Design:	A single-arm pre/post-study
Central Hypotheses:	Our central hypotheses are that students and parents who view the risk communications will be more likely to have increased COVID-19 testing and vaccine uptake.
Primary Objectives:	
• To determine if implementing three COVID-19 education comic books for children and two COVID-19 education videos for parents will increase COVID-19 testing and vaccine uptake in children.
Secondary Objectives:	
• To determine if implementing three COVID-19 education comics books for children and two COVID-19 education videos for parents will increase physical activity, improve sleep, increase emotional regulation in children.• To determine if implementing three COVID-19 education comics books for children and two COVID-19 education videos for parents will increase physical activity, improve sleep, decrease depression and anxiety in parents
Population:	Children ages 3-5 enrolled in the Early Learning program in Yakima School District
Study Size:	Early Learning is an ancillary study with no defined sample size. We will enroll and recruit participants for a total of eight weeks
Primary Outcome Measurements:	
A. COVID-19 testing data available through self-reported surveyB. COVID-19 vaccine data available through self-reported survey
Study Duration:	11 months – September 2022- August 2023

3. Study Design

The ancillary study runs parallel with the larger ROSSEY RCT. Recruitment, enrollment, and baseline assessment are expected to last two months (September-November 2022). Enrolled participants will not receive the comic book and parent video series until after completion of the ROSSEY RCT Post 1 follow-up Survey to not bias the data of older siblings participating in the ROSSEY RCT. A follow-up assessment for Early Learning participants is anticipated to take place 10 months after the launch of recruitment (July-August 2023)

4. Sample size and power

Early Learning is an ancillary study of 50 participants. We will enroll and recruit participants for a total of eight weeks.

Enrollment Criteria

Parent/Guardian eligibility criteria for participation in the study include:

- Must have a child attending the Early Learning Program in the Yakima School District
- Must be able to provide informed consent and legal guardian assent either virtually, on the telephone, or in-person.
- Must have a permanent mailing address available for study staff to mail necessary materials OR a working email address.

5. Population and Data Source

Participants enrolled in the ROSSEY Study: 50 children and parents from the Yakima School District. Any participants subsequently found to be ineligible will be removed. The data sources for the primary analyses are COVID testing results received from the school administration and the survey data as entered in REDCap. The COVID vaccination status data is obtained through the parent and child surveys, completed in REDCap.

6. Presentation of analyses

For each of the continuous outcomes (including the primary outcome), the mean and standard deviation will be presented pre/post intervention and p value. For binary outcomes, the percentage and frequency of children in the outcome category of interest (e.g., percentage vaccinated) will be presented pre/post and p value.

7. Outcome Definitions

a. Primary Outcomes

The two co-primary outcomes of the trial are COVID-19 testing and COVID-19 vaccine uptake. COVID-19 data are captured through school testing and self-reported survey, and COVID-19 vaccine uptake data are captured through self-reported survey. All children and parent data will be included in the intention-to-treat analysis.

COVID-19 testing: Health reports from the school are provided for the 2022-2023 school year that list positive covid test results of study participants with the date of testing and the school of attendance. Positive test results for COVID will be a binary, yes/no variable.

COVID-19 vaccine uptake: Parents are asked at enrollment to report their vaccination status and their child's vaccination status. At post survey, the parent is asked to report if they or their child have received any COVID-19 vaccine or booster since enrollment. Vaccination status will be a binary, yes/no variable.

b. Secondary Outcomes

Secondary outcomes for the trial include the following outcomes from the PROMIS – Pediatric and Parent Proxy Instruments. The PROMIS instruments used are Children's physical activity (PA), sleep, stress, depression, and anxiety. Parents' PA, sleep, stress, depression and anxiety. The final score is represented by the T-score, a standardized score with a mean of 50 and a standard deviation (SD) of 10.

The outcome measures will be collected at pre-and post-assessment.

8. Primary exposure definition

Receiving the educational materials: three comic books and two graphic motion videos.

9. Interim analysis plan

For this study, there was no interim analysis.

10. Multiple testing

We will adjust for multiple testing by controlling FDR.

11. Missing Data

We will inspect missing data mechanisms and the amount of missing data. We will conduct an additional sensitivity analysis with multiple imputations using multivariate imputation with chained equations (MICE) approach. We will report the amount of missing data and apply appropriate methods to account for the missing data.

12. Planned Statistical Analyses

a. Baseline Demographics

The baseline characteristics of enrolled participants will be summarized in a table.

b. Efficacy Analyses Overview

Pre/post-survey outcome analyses will be conducted after all participants have been contacted and the survey is closed with missing responses marked as loss to follow-up.

- 1) **Descriptive Analyses:** Positive COVID test results will be summarized by counts. Vaccine status and COVID testing results will be presented as counts and percentages. Continuous variables will be summarized by mean, standard deviation (SD), and median (IQR). Secondary outcomes will be compared using Chi-squared tests.
- 2) **Primary Objectives:** The primary analysis of vaccine uptake and COVID testing will be conducted using a chi-squared test using $\alpha = 0.05$ and report pre/post changes over time.
- 3) **Secondary outcomes:** The secondary outcomes for the trial include measures from the PROMIS – Pediatric and Parent Proxy Instruments. The PROMIS instruments used are children's PA, sleep, stress, depression, and anxiety and parents' PA, sleep, stress, depression, and anxiety.

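### The SAP names inconsistent sources for the COVID-19 testing co-primary and has no rule for which source supplies the pre value and which the post value

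*SAP*

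**What the plan says.** SAP 7a states that "The two co-primary outcomes of the trial are COVID-19 testing and COVID-19 vaccine uptake". SAP 12b tests both by chi-squared at 0.05 and reports pre/post change. The source of the testing outcome appears in four places:

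- SAP 2, Primary Outcome Measurements: "COVID-19 testing data available through self-reported" survey. No other source is named.
- SAP 5: "The data sources for the primary analyses are COVID testing results received from the school administration and the survey data as entered in REDCap".
- SAP 7a, opening paragraph: "COVID-19 data are captured through school testing and self-reported survey".
- SAP 7a, definition of the testing outcome: "Health reports from the school are provided for the 2022-2023 school year that list positive covid test results of study participants". Each entry is dated and names the child's school. The derived variable follows: "Positive test results for COVID will be a binary, yes/no variable". The survey is not mentioned here.

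On survey content, Protocol VI (Follow-up Survey) lists contact and demographic updates, the child's vaccination status, and "mitigation behaviors and the secondary outcome measures". Testing is not named. The baseline survey section of Protocol VI is still a placeholder.

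**The concern.** The sections do not agree on what data form a co-primary outcome. Neither document says which source gives the pre value, which gives the post value, or what happens when the two disagree or one is missing. The vaccine outcome in SAP 7a shows what is absent: it states who is asked, at which surveys, and over what period.

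The gap matters because the sources record different things. A parent can report any test, with any result, done anywhere. The school list shows a child only if the result was positive and fell in the 2022-2023 school year, so a child who tested negative looks the same as one never tested. The stated objective is testing uptake. In a single-arm study, any difference in how completely tests are recorded before and after would be read as an effect. The choice of source would also remain open once the data have been seen.

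**Working it through.** The plan gives no figure to reproduce, so the check is mainly a comparison of passages.

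**1. Sources.** The four statements give three sets: survey only (SAP 2), school and survey (SAP 5 and the opening of 7a), school only (the 7a definition).

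**2. What the school list can cover.** Two timelines appear.
- Protocol VI puts distribution of materials within two weeks of the end of the main trial's final assessment, December 2023, and follow-up contact 6 weeks later. The 2022-2023 school year is then over, so every school result precedes the intervention. Only the survey could record a later test.
- Protocol I and SAP 3 put follow-up in July-August 2023. School results could then enter the later value.

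On the early side, recruitment in September-November 2022 lies inside the reported school year and school results are dated. The list could therefore hold some results from before a child enrolled.

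**3. What the survey can cover.** Testing is not named in the follow-up list, unless it is meant as a mitigation behaviour. Baseline content cannot be checked, because that section is unwritten.

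**4. Illustration of size.** All rates here are assumptions; none comes from the documents. Let T be the true share of children tested, unchanged from pre to post (0.3 to 0.7). Let s be the share of tested children that the survey records (0.6 to 0.9), and c the share that appear on the positives-only list (0.1 to 0.2). Recording by the two sources is taken as independent.

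| Source, pre then post | Apparent change | Smallest | Largest |
|---|---|---|---|
| Survey, survey | T·s − T·s | 0 | 0 |
| Survey, survey or list | T[1 − (1−s)(1−c)] − T·s = T(1−s)c | 0.3×0.1×0.1 = +0.3 points | 0.7×0.4×0.2 = +5.6 points |
| List, survey | T(s − c) | 0.3×(0.6−0.2) = +12 points | 0.7×(0.9−0.1) = +56 points |
| Survey, list | T(c − s) | −12 points | −56 points |
| List, list, with December 2023 distribution | 0 − T·c | 0.3×0.1 = −3 points | 0.7×0.2 = −14 points |

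In the last row the list has no entries after the materials go out, so its post value is zero by construction. Rows two and four need school data at follow-up, so they arise only on the July-August 2023 timeline.

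**5. Effect on the test.** Take n = 50 at each time (SAP 4), a two-sided 0.05 test and pre and post as independent samples. With p̄ the mean of p1 and p2, the chance of p < 0.05 is about Φ{[|p2−p1|√n − 1.96√(2p̄(1−p̄))] / √(p1(1−p1)+p2(1−p2))}.
- List then survey, T = 0.3, c = 0.2, s = 0.9: p1 = 0.06, p2 = 0.27, p̄ = 0.165. This is Φ[(1.485 − 1.029)/0.503] = Φ(0.91) = 82%.
- Same, T = 0.5: 0.10 against 0.45, 98%.
- One source at both times (s = 0.9): simulated rejection is 5.0% to 5.5% for T of 0.3, 0.5 and 0.7.

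The same children are measured twice, so these percentages are only a guide.

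**The case against.** The strongest reply is that no change of source is planned. SAP 12b describes the outcome analyses as pre/post survey analyses, run once the survey closes. With SAP 2, that points to the survey at both times, where the artefact is zero. This stands as evidence of intent, but the definition in SAP 7a does not adopt it and describes school reports instead.

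A second reply is that the sections are closer than they look. The school paragraph in SAP 7a may only be detail on one of two sources, and SAP 5 may mean school for testing and survey for vaccination. The first reading still leaves two sources and no rule. The second makes testing school-only, which contradicts SAP 2 directly.

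Several stronger readings are tempting but unsupported:
- A reader might infer that a value from before enrolment can come only from the survey. Recruitment falls inside the reported school year and results are dated, so some could come from the school.
- A reader might infer that school data will enter the follow-up value. On the December 2023 date they cannot record anything after the materials.
- A reader might assume that the list captures a large share of tested children, say 20% to 60%, and derive a false rise from it. A positives-only list gives no basis for that range.

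It is also fair that any single consistent rule would cure the contradiction; the survey is not the only possible choice.

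**Conclusion.** The concern holds as an inconsistency between sections on a co-primary outcome, with no rule for the pre and post sources. It should be corrected before analysis. The school definition as written cannot give a like-for-like pre/post measure of testing: it records positives only, in one school year, with no pre or post window.

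A reader might go further and conclude that the reported change will be an artefact of a source switch. The documents do not support that. They leave a switch possible without planning one, and they contain no rates from which a size could be derived. The figures above rest wholly on the assumed T, s and c and on independent recording. They show that the size depends on the rule chosen: small if the list only supplements the survey, large if one source replaces the other. If parents recall positive tests better than negative ones, supplementing would add less still.

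Whether school data can reach the period after the intervention depends on the distribution and follow-up dates, which conflict and must be reconciled.

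**What to change.** Before analysis:

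1. State one source in SAP 2, 5 and 7a: the parent survey at baseline and at follow-up, with the same yes/no question on whether the child was tested and the same look-back length. This follows SAP 2, and the survey is the source that can record negative tests and reach both sides of the intervention on either timeline.
2. Report school positives separately as descriptive counts. Do not use them to fill in or overwrite a survey answer.
3. Confirm that the testing question was asked at both times, and name it in the protocol's baseline and follow-up survey sections.
4. If it was not asked at baseline, report testing descriptively with no pre/post test.
5. Reconcile the distribution and follow-up dates in Protocol I, Protocol VI and SAP 3.

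The cost is mainly wording. Tests that parents forget are not recovered from the school list. The protocol is dated 1/03/24 and baseline was planned for September-November 2022, so if baseline ran on schedule a missing question cannot now be added. The study would then lose the pre/post test on this co-primary.
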